
Main selection criteria:
	
Inclusion criteria:
 
Inclusion criteria at screening
 
I 01. Written informed consent;
 
I 02. 18 years of age or older
 
I 03. Patient admitted to the hospital or had urgent visit to emergency department or heart failure unit/coronary care center for Congestive Heart Failure (CHF), defined by:
 
 
- Presence of ≥2 of the following clinical signs and symptoms of congestion: jugular venous distension, pitting edema in lower extremities greater than trace, dyspnea, rales heard on auscultation, radiographic pulmonary congestion, weight gain above historical dry weight of at least 5 lbs. (2.27 kg)
 
 
AND
 
 
- Requiring treatment with IV diuretics
 
 
I 04. Estimated glomerular filtration rate (eGFR) ≥30 mL/min/1.73m^2 at the screening or randomization visit by the 4-variable Modification of Diet in Renal Disease (MDRD) equation
 
I 05. Female subject must use a double contraception method during the study including a highly effective method of birth control, except if she has undergone sterilization at least 3 months earlier or is postmenopausal.
 
I 06. Male participants, unless vasectomized and confirmed sterile by sperm analysis, must use condoms during the study and refrain from donating sperm up to 90 days after the day of last dose. If the patient has a female partner of childbearing potential, the patient must wear a condom and female partner must use at least a highly effective method of birth control during the study treatment period and the follow-up period.
 
Inclusion criteria at randomization
 
I 07. Transitioning from intravenous (IV) to oral diuretics and

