- b For hospitalized patients eligible for discharge on study day D1, the timing of discharge from the hospital is at the discretion of the treating physician but should not be less than 6 hours following the administration of study drug. Patients that are not eligible for discharge, may complete all or part of the study as inpatients (hospital or other appropriate unit). For patients returning to the day unit for D1, they should also stay in the unit and have their vital signs assessed every 2 hours after IMP administration and discharged not sooner than 6 hours after IMP administration. Laboratory tests may be performed in the hospital or outpatient unit, depending on whether the patient remains hospitalized.
- c Day 1 only. IRT contact for randomization. The time is indicative, as randomization should take place after review of inclusion/exclusion criteria
- e Meal to be taken within 15 minutes after administration of study drug.
- f Deuterium oxide intake should take place after blood collection for baseline measurements.
- g Vital signs: including heart rate, systolic and diastolic blood pressure measured after 10 minutes in supine or sitting (preferably sitting) resting position. Orthostatic changes in blood pressure will be assessed once for all patients not limited by mobility issues (assess BP when supine or sitting for 10 mins and after 3 mins standing). For patients returning to the day unit for D1, they should stay in the unit. Their vital signs will be assessed at baseline and every 2 hours after administration of IMP. Patients should be monitored for at least 6 hours prior to discharge from the unit.
- h For Visits 2 (Day 1) and 5 (Day 14±1), those samples will be obtained as part of the Hemoconcentration sampling, thus no additional samples for Hematology or Biochemistry are required. It is indicated here as a reminder that baseline hematology and biochemistry is done on Visits 2 and 5. For all other Visits, Hematology and Biochemistry samples are to be obtained as indicated.
- i β-HCG performed at screening and D14 only
- j Indicative time. Those samples can be obtained at the same time as the other samples are collected, eg, biochemistry.
- k Pharmacokinetic samples will not be collected for cohort 3.
- l Hemoconcentration is determined using the following: Hematocrit, hemoglobin, total protein and albumin. Baseline biochemistry (creatinine, urea, electrolytes) and complete blood count will also be determined from those samples

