### 8.2 INCLUSION CRITERIA

#### 8.2.1 Inclusion criteria at screening

- I 01. Written informed consent;
- I 02. 18 years of age or older
- I 03. Patient admitted to the hospital or had urgent visit to emergency department or heart failure unit/clinic or infusion center for Congestive Heart Failure (CHF), defined by:

- Presence of  $\geq 2$  of the following clinical signs and symptoms of congestion: jugular vein distension, pitting edema in lower extremities greater than trace, dyspnea, rales heard on auscultation, radiographic pulmonary congestion, weight gain above historical dry weight of at least 5 lbs (2.27 kg)

AND

- Requiring treatment with IV diuretics

- I 04. Estimated glomerular filtration rate (eGFR)  $\geq 30$  ml/min/1.73m^2 at the screening or randomization visit by the 4 variable Modification of Diet in Renal Disease (MDRD) equation
- I 05. Female subject must use a double contraception method during the study including a highly effective method of birth control, except if she has undergone sterilization at least 3 months earlier or is postmenopausal.
- I 06. Male participants, unless vasectomized and confirmed sterile by sperm analysis, must use condoms during the study and refrain from donating sperm up to 90 days after the day of last dose. If the patient has a female partner of childbearing potential, the patient must wear a condom and female partner must use at least 1 highly effective method of birth control

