**Table 3 - List of schedule of events for the hemoconcentration and total body water assessment procedure**

Time points (from IMP intake)	Day / Time	Procedure
	D1 and D14	
T0 (-2.5 H)	7:30 am	Physical exam, vitals signs, blood and urine samples, ECG Deuterium oxide intake (immediately after blood sample collection)
T1 (- 2 H)	8:00 am	Patient assumes semi-recumbent position
T2 (-1 H)	9:00 am	Hemoconcentration samples (Hematocrit, Hemoglobin, Albumin, and Total Protein). Patient allowed mobilizing.
T3 (0 H)	10:00 am	IMP administered followed by breakfast
T4 (1 H)	11:00 am	Blood sample for deuterium oxide

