### 10.2 SAFETY

Assessments for safety include AEs, clinical laboratory assessments, physical examination, ECG, weight and vital signs. An independent DMC will meet on a regular basis to review accumulating clinical trial safety data. Enrollment in Cohort 2 will only proceed following review of cases in Cohort 1 by the DMC, and similarly enrollment in Cohort 3 will only proceed following review of cases in Cohort 2 by the DMC.

Serum creatinine will be assessed at Baseline (Day 1, Visit 1) and on-site Visits 2, 3 and 4 (in cohort 3 on-site visit 4 was eliminated precluding any serum collection). A central laboratory will analyze samples and estimate change from Baseline in serum creatinine and eGFR. Renal safety will also be assessed on a regular basis by an independent expert, who may also be a member of the DMC.

The following safety endpoints will be assessed:

- Adverse events, AEs leading to discontinuation from the IMP, adverse events of special interest (AESIs), Events of Special Interest (EOSIs), SAEs and deaths
- Hypoglycemia (severe, documented symptomatic, or asymptomatic)
- Clinical laboratory results, vital signs and ECG results

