### 11.3.5 Guidelines for management of specific laboratory abnormalities

Once the subject is included in the clinical trial, the following laboratory abnormalities must be monitored, documented, and managed according to the related decision charts in [Appendix B](#).

- Neutropenia
- Thrombocytopenia
- ALT increase
- Creatine phosphokinase (CPK) increase, suspected to be on non-cardiac origin and not related to an intensive physical activity

Renal function and the extent of renal injury that is commonly precipitated by intensive diuretic treatment in this patient population will be reviewed on a frequent basis by an independent renal expert, member of the Data Monitoring Committee (DMC), who shall communicate potential issues to the Sponsor. Overall renal safety in Cohorts 1 and 2 will be assessed by the DMC.

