#### 13.1.2 Inclusion procedures

Inclusion procedures will be carried out during Screening (D-21 to D-1) or D1, as appropriate for each patient. Those will include the investigations listed in the study flow chart ([Section 1.2](#)) and detailed in [Section 10.2](#).

Baseline parameters may be rechecked once, at the Investigator's discretion. Results of a rechecked value should be known before the inclusion. The last value should be considered as the baseline value and reported in the case report form.

Prior to final inclusion and randomization, all patients must have completed the last planned IV administration (bolus or infusion), and *either* have commenced oral diuretic therapy *or* have a clear and documented plan to commence oral diuretic therapy. Patients may be discharged and return for Day 1 procedures within seven (7) days from discontinuation of IV diuretic administration.

Final inclusion and randomization, as appropriate, will be performed just before commencement of procedures on Day 1. Each patient will receive an incremental identification number corresponding to his/her order of enrollment in the study.

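### I 04 can be met on a creatinine taken before or during IV diuresis; no later value is required before randomization, so a patient below eGFR 30 on Day 1 can be randomized and dosed

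*Protocol*

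**What the plan says.** - **The limit.** Protocol 8.2.1 lists I 04 among the criteria at screening: eGFR of at least 30 "at the screening or randomization visit by the 4 variable Modification of Diet in Renal Disease (MDRD) equation". The clinical trial summary has the same rule. Protocol 4.2.2 states that patients below 30 will be excluded.
- **The windows.** Screening runs from Day -21 to Day -1 and may extend to randomization on Day 1 (13.1.1). The summary places it during the admission or urgent visit treated with IV diuretics. Randomization follows within 7 days of stopping them.
- **Criteria at randomization.** I 07 and I 08 (8.2.2) cover the switch to oral diuretics and hemodynamic stability. Neither mentions renal function.
- **Later values.** Section 13.1.2 says "Baseline parameters may be rechecked once", at the investigator's discretion. Footnote a to the flow charts lets the laboratory result closest to Day 1 govern when results disagree.
- **Order on Day 1.** Section 13.1.2: "Final inclusion and randomization, as appropriate, will be performed just before commencement of procedures on Day 1". For Day 1 hematology and biochemistry, footnote h to the cohort 3 period flow chart (1.5) says "those samples will be obtained as part of the Hemoconcentration sampling". Table 3 puts that draw, "Hemoconcentration samples (Hematocrit, Hemoglobin, Albumin, and Total Protein"), one hour before dosing.
- **Laboratory.** Section 10.2: "A central laboratory will analyze samples and estimate change from Baseline in serum creatinine and eGFR".

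**The concern.** An eligibility limit protects patients only if the value behind it describes them when they are randomized. Here renal function is expected to move between the two times. Protocol 4.2.2 calls this a period of flux in which the kidney is vulnerable, and notes that SGLT inhibition itself lowers GFR. Section 11.3.5 refers to "the extent of renal injury that is commonly precipitated by intensive diuretic treatment in this patient population". The value used for I 04 may predate the end of that treatment.

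Other hazards are tied to randomization: systolic pressure (I 08), genitourinary infection (E 15) and diabetic limb complications (E 18). Renal function is not.

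If the Day 1 result comes back below 30, the patient is already randomized and may already be dosed. No stated eGFR floor stops treatment. Section 7.2.1 offers a persistent fall of more than 50% as an example of when to stop; from a Day 1 value of 28, that means below 14.

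**Working it through.** The plan gives no figure to reproduce. The check has two parts.

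**1. Timing in cohort 3 (Protocol 1.4, 1.5, 10.1.2.1, 13.1.2)**

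| Event | Time |
|---|---|
| Screening creatinine | Day -21 to Day -1, or Day 1 |
| IV diuretics stop | up to 7 days before randomization |
| Randomization | Day 1, -3H (7 am, indicative) |
| Day 1 biochemistry drawn | Day 1, -1H (9 am) |
| First dose | Day 1, 0H (10 am) |
| Next scheduled creatinine | Day 6 to 8 |

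The scheduled Day 1 sample follows randomization by about 2 hours and precedes the dose by 1 hour. The 7 am slot is only indicative, but 13.1.2 fixes the same order in words. Nothing is scheduled between screening and Day 1. The oldest admissible value is 21 days old. Since IV diuretics must have ended no more than 7 days before Day 1, such a sample was taken at least 21 - 7 = 14 days before they ended.

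**2. How many patients could cross the limit**

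The MDRD equation in Protocol 8.1 makes eGFR proportional to creatinine to the power -1.154 when age, sex and race are fixed. A creatinine rise by factor r therefore multiplies eGFR by r^-1.154:

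- r = 1.10: a screening eGFR of 30 becomes 26.9; a screening value of at least 33.5 is needed to stay at 30.
- r = 1.20: 30 becomes 24.3; at least 37.0 is needed.
- r = 1.30: 30 becomes 22.2; at least 40.6 is needed.

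For a population estimate, only one input comes from the documents: about 50% of patients may be below 60 (4.2.2), taken here as a median of 60. The rest are assumptions: screening eGFR Normal(60, SD 20); log creatinine change from screening to Day 1 with mean 0 and SD s; no test in between for anyone.

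A patient screened at g falls below 30 when the log creatinine change exceeds ln(g/30)/1.154, which has probability 1 - Φ(ln(g/30)/(1.154 s)). With s = 0.20:

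- g = 35: ln(35/30)/1.154 = 0.134; 0.134/0.20 = 0.67; probability about 25%.
- g = 60: ln(2)/1.154 = 0.601; 0.601/0.20 = 3.0; probability about 0.1%.

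Averaging over all g of at least 30, and dividing by the probability of passing screening:

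| s | Below 30 on Day 1 | Of 34 in cohort 3 | Share of these at 25 to 30 |
|---|---|---|---|
| 0.10 | 1.24% | 0.4 | 94% |
| 0.20 | 3.27% | 1.1 | 73% |
| 0.30 | 6.34% | 2.2 | 58% |

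Sensitivity, for s = 0.10, 0.20 and 0.30:

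- eGFR SD 15: 0.77%, 2.47%, 5.61%.
- eGFR SD 25: 1.46%, 3.57%, 6.47%.
- SD 20 with a 10% mean creatinine rise: 3.59%, 6.14%, 9.89%, which is 1.2, 2.1 and 3.4 of 34.

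**The case against.** The strongest reply is that the protocol already allows what is being asked for. Screening may be done on Day 1. Rechecked results must be known before inclusion, and the last one counts (13.1.2). All criteria are checked again on Day 1 before randomization (9.4), and laboratory tests may be done in the hospital or outpatient unit (1.5, footnote b). The central-laboratory sentence in 10.2 concerns change from baseline and does not say that the eligibility value must be central. All of this stands. It shows that a later value is possible, not that one is required, and footnote a only chooses among results that already exist.

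Two stronger readings are tempting, and the documents support neither:

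- A reader might infer that only the screening value can be known at randomization. The provisions above allow a known Day 1 or rechecked result.
- A reader might infer that a patient below 30 at screening who recovers is shut out. Section 13.1.1 allows one recheck of any screening parameter, and 8.1 and 9.4 allow re-screening.

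It is also fair to say that a 21-day-old value is the worst case; that the windows were widened on purpose, for flexibility (Appendix F); that most modelled crossings are marginal; and that 4.2.2 reports 400 mg as well tolerated for 7 days in stage 3 CKD. Investigator and DMC discretion to stop treatment, the renal expert's frequent review and at least 6 hours of monitoring on Day 1 limit the harm. None of these requires a creatinine result before the first dose.

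**Conclusion.** The point holds as a gap in the eligibility rule: a current renal value is allowed but not required, and the scheduled Day 1 sample comes too late to serve as the check. As written, I 04 can admit patients whom 4.2.2 says will be excluded.

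The size is small. Cohort 3 is the relevant denominator because the current amendment changes that cohort and is implemented only in the US, where it is run. With no average change in creatinine, about 0.4 to 2.2 of its 34 patients would be below 30 on Day 1. Within each scenario this is an upper bound, because it supposes that nobody is tested between screening and Day 1. An average creatinine rise would push the figure up, as the sensitivity run shows. The spread of eGFR and of creatinine change is assumed, not taken from the documents.

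This is a matter of patient protection. Eligibility is settled before allocation, so the comparison of arms is not biased. The change is worth making because it is specific and cheap.

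**What to change.** In I 04 (Protocol 8.2.1 and the clinical trial summary), replace the choice between two visits with: *on the latest creatinine obtained before randomization (local laboratory acceptable), drawn no more than 72 hours before randomization*. List the criterion in 8.2.2 beside I 07 and I 08. The 72 hours is a proposal with no basis in the documents; any short stated window would serve.

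An existing hospital result inside the window is enough, so same-day screening and randomization can continue. The Day 1 sample stays where it is, as the baseline.

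The cost is one routine local creatinine for patients without a recent result, and possibly one or two more screen failures in cohort 3.

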### 8.2.2 Inclusion criteria at randomization

- I 07. Transitioning from intravenous (IV) to oral diuretics and oral diuretic treatment has been prescribed or administered
- I 08. Hemodynamically stable, defined as:
- SBP  $\geq 100$  mmHg with no requirement for IV inotropes or IV vasodilators

### 8.3 EXCLUSION CRITERIA

- E 01. History of Type 1 diabetes mellitus
- E 02. Appears unlikely or unable to participate in the required study procedures, as assessed by the study Investigator, study coordinator, or designee (ex: clinically-significant psychiatric, addictive, or neurological disease), or sectioned due to an official or court order
- E 03. Tachyarrhythmia with ventricular rate  $> 130$  bpm at screening, unless determined to be clinically stable by the investigator current admission for worsening heart failure primarily triggered by causes such as acute coronary syndrome, pulmonary embolism, cerebrovascular accident, heart valve disorders (such as severe aortic stenosis), as determined by the Investigator

- E 04. Clinically significant myocardial infarction (MI) within past 1 month as determined by Investigator and with objective evidence from ECG, and/or cardiac imaging and/or coronary angiography. Small isolated elevations in troponin that often accompany HF hospitalization are not an exclusion, nor are clinically significant MIs that have been re-vascularized without complications
- E 05. Patients who recently had or scheduled to have cardiac interventions may be eligible if:
- Stable 48 hours post procedure AND
  - Have diuretic treatment planned for the duration of treatment in this study
- E 06. Current use of or recent suspension of digoxin therapy with high levels of digoxin (level should be obtained and must be <1.2 ng/mL) at screening.
- E 07. History of heart or kidney transplant
- E 08. Diagnosis of hypertrophic obstructive cardiomyopathy
- E 09. End-stage HF defined as requiring left ventricular assist device insertion, intra-aortic balloon placement (IABP), or any type of mechanical support during the study period
- E 10. Pregnancy (demonstrated by serum pregnancy test at screening), breast-feeding, or inability or refusal to undergo pregnancy testing
- E 11. Use of any investigational drug(s) or prohibited therapy or sodium-glucose co-transporter 2 (SGLT2) inhibitor 5 half-lives prior to screening
- E 12. Patients with moderate or severe respiratory, hepatic, neurological, psychiatric, active malignant tumor or other major systemic disease (including any diseases with evidence of malabsorption), making implementation of the protocol and/or the interpretation of the study results difficult
- E 13. Known allergies, hypersensitivity, or intolerance to sotagliflozin or any inactive component of sotagliflozin or placebo (i.e., microcrystalline cellulose, croscarmellose sodium [disintegrant], talc, silicon dioxide, and magnesium stearate [non-bovine]), unless the reaction is deemed irrelevant to the study by the PI
- E 14. Laboratory findings at the Screening Visit:
- a) Alanine aminotransferase (ALT) or aspartate aminotransferase (AST) >3 times the upper limit of the normal laboratory range (ULN) (1 repeat lab allowed)
  - b) Total bilirubin >1.7 times the ULN (except in case of Gilbert's syndrome) (1 repeat lab allowed)
  - c) Amylase and/or lipase > 3 times the ULN (1 repeat lab allowed)
- E 15. Patients with a severe or persistent in spite of optimal treatment genitourinary tract infection at time of randomization.

- E 16. Patient is the investigator or any sub-investigator, research assistant, pharmacist, study coordinator, other staff or relative thereof directly involved in the conduct of the protocol

**8.3.1 Additional exclusion criteria for patients with diabetes**

- E 17. History of diabetic ketoacidosis or non-ketotic hyperosmolar coma within 3 months prior to the screening visit
- E 18. Lower extremity diabetic complications (such as skin ulcers, infection, osteomyelitis and gangrene) identified during the Screening period, and still requiring treatment at Randomization

## 9 STUDY TREATMENTS

### 9.1 INVESTIGATIONAL MEDICINAL PRODUCTS (IMP)

The IMPs are sotagliflozin 400 mg, sotagliflozin 200 mg, and matching placebo. Patients will be provided with treatment kit according to the cohort number and the arm allocation in the cohort for the Double -Blind Treatment Period:

- Placebo kit: containing placebo tablets
- Or Sotagliflozin 200 mg kits: containing placebo tablets and Sotagliflozin 200 mg tablets
- Or Sotagliflozin 400 mg tablets: containing Sotagliflozin 200 mg tablets.

**Table 2 - Summary of investigational medicinal products**

IMP:	Sotagliflozin 200 mg	Sotagliflozin 400 mg	Placebo group
Name of IMP	Sotagliflozin (SAR439954)	Sotagliflozin (SAR439954)	Placebo
Pharmaceutical Form	Sotagliflozin (SAR439954) will be supplied as 200 mg tablets	Sotagliflozin (SAR439954) will be supplied as 200 mg tablets	Placebo will be supplied as tablets (identical to sotagliflozin in appearance)
Dose, timing, and route of administration	Sotagliflozin 200 mg group: One 200 mg tablet, taken orally once daily, before the first meal of the day and One placebo tablet, taken orally once daily, before first meal of the day	Sotagliflozin 400 mg group: Two 200 mg tablets, taken orally once daily, before first meal of the day	Placebo group: Two placebo tablets, taken orally once daily, before first meal of the day
Duration of treatment	14 days double-blind Treatment Period following Randomization	14 days double-blind Treatment Period following Randomization	14 days double-blind Treatment Period following Randomization
Storage conditions	Store between +15 °C and +30 °C (59 °F and 86 °F)		

### 9.2 NON-INVESTIGATIONAL MEDICINAL PRODUCTS

#### **I-albumin:**

Supplied as  $\leq 25\mu\text{Ci}$  in 1mL, at date of calibration. Each mL contains:

- 10mg human albumin (non-reactive to HBsAg)
- 16mg sodium dibasic phosphate
- 1.6mg sodium monobasic phosphate

- 0.4mg guanidine hydrochloride
- Sodium chloride
- 9mg benzyl alcohol

Route of administration: IV, see Laboratory manual for detailed instructions.

Dose: 10mg ( $\leq 25$   $\mu$ Ci)

